Study Protocol

Official Title: A Story-Based Digital Game to Reduce Anxiety and Improve Treatment Compliance in Hemodialysis Patients: A Randomized Controlled Trial

NCT Number: To be assigned

Ethics Committee Approval Number: E.888577

Study Period: March 2025 – April 2025

Study Protocol

Title: A Story-Based Digital Game to Reduce Anxiety and Improve Treatment Compliance in Hemodialysis Patients

Protocol Version: 1.0

Protocol Date: March 1, 2025

Principal Investigator(s): [name] [name], Assoc. [name]

Institution: Suleyman Demirel University, Department of Nursing

Sponsor: Suleyman Demirel University BAP Coordination Unit

1. Project and Study Dates

Project Duration (BAP-Funded): January 3, 2025 – June 17, 2025

Study Implementation Dates: March 1, 2025 – April 30, 2025

2. Ethical Approval

The study protocol was reviewed and approved by the Ethics Committee of Suleyman Demirel

Ethics Approval Number: E.888577

Ethics Approval Date: 11.15.2024

3. Background and Rationale

Hemodialysis patients often face psychological stress, low adherence, and dietary mismanagement. This study introduces a story-based digital game to educate and emotionally support patients during dialysis sessions.

4. Objectives

- To evaluate the impact of a digital game on treatment adherence
- To assess improvements in dietary knowledge
- To determine reductions in anxiety levels among participants

5. Study Design

This is a single-center, single-blinded randomized controlled trial. Participants are assigned to either the intervention (digital game) group or control (standard care) group. Sessions were separated to prevent contamination, and the statistician was blinded to group assignment.

6. Study Population

Inclusion Criteria:

- Age 18–80 years
- At least 6 months on hemodialysis
- Literate
- Consent provided

Exclusion Criteria:

- Cognitive impairment or refusal to consent

7. Intervention Description

The digital game features a fictional character beginning dialysis. Patients mentor this character through challenges, reinforcing their own knowledge on diet, fluid management, and self-care. Each session lasts 10–15 minutes.

8. Outcome Measures

Primary:

- End-Stage Renal Disease Adherence Scale
- Hemodialysis Patients' Diet Knowledge Scale
- State Anxiety Scale

Secondary:

- Game Experience Questionnaire (GAMEX)

9. Statistical Analysis

Data will be analyzed per the Statistical Analysis Plan (SAP). Non-parametric methods (Mann-Whitney U, Friedman test) and Bonferroni-corrected Wilcoxon tests will be used. SPSS v26.0 will be employed.

10. Informed Consent and Confidentiality

Informed consent will be obtained from all participants prior to enrollment. Participant confidentiality will be ensured. All data will be anonymized.

11. Monitoring and Reporting

Adverse events will be monitored throughout the study. All protocol deviations and issues will be documented and reported.

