### 3. Study Design Summary

This study follows a single-center, single-blinded, randomized controlled design with two parallel arms: an intervention group and a control group. Patients were randomized (1:1) to either group.

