### 4. Statistical Methods

The analysis will follow the intention-to-treat principle. Descriptive statistics will be calculated for all variables. Continuous variables will be presented as mean  $\pm$  standard deviation, and categorical variables as frequencies and percentages.

Between-group comparisons of continuous variables will use the Mann–Whitney U test. Repeated measures within each group will be analyzed using the Friedman test. Post hoc analyses will be conducted using the Wilcoxon signed-rank test with Bonferroni correction where applicable. Chi-square or Fisher's exact tests will be used for categorical data.

Statistical significance will be determined at a two-sided alpha level of 0.05.

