## **6. Assumptions and Adjustments**

Given the small sample size and the ordinal nature of the scales used, non-parametric tests were selected. Multiple testing adjustments will be made using Bonferroni correction. Data will be analyzed using IBM SPSS v26.0.

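### Does the unexplained separation of sessions in Protocol section 5 call the patient-level comparison into question?

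*Protocol*

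**What the plan says.** Protocol section 5 describes a single-centre trial in which "Participants are assigned to either the intervention (digital game) group or control (standard care) group", and adds: "Sessions were separated to prevent contamination, and the statistician was blinded to group assignment". The word *session* has two uses elsewhere in the protocol. Section 3 says the game is meant to "educate and emotionally support patients during dialysis sessions", which refers to dialysis. Section 7, describing the game, says "Each session lasts 10–15 minutes".

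SAP section 3 makes the patient the unit of randomisation: "Patients were randomized (1:1) to either group". It mentions no stratification or clustering by session, shift or day. SAP section 4 gives the test: "Between-group comparisons of continuous variables will use the Mann–Whitney U test". SAP section 6 adds: "Multiple testing adjustments will be made using Bonferroni correction". SAP section 5 lists adherence, dietary knowledge, anxiety and game experience. No session or shift variable is mentioned.

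**The concern.** Patients usually share a dialysis session with others. If the separated sessions were dialysis sessions, simple 1:1 randomisation of patients would not produce that arrangement. Someone must have placed patients in arm-specific sessions, and the documents do not describe that step.

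Two things would then be at stake. First, a difference between arms could reflect staff, time of day or other shared conditions as well as the game. Second, patients in one session would be correlated, while the Mann–Whitney test treats them as independent, so its error rate could exceed 5%. Bonferroni lowers the level of each test but does not remove the correlation. Without a session variable, a reader could not tell whether any of this applied.

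**Working it through.** The plan states no figure to reproduce on this point. The sample size is described only as small. Every size, session count and correlation below is therefore an assumption.

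**1. What the text settles.** Both documents name the patient as the unit assigned. Section 5 does not say what was separated. The readings that fit are:
- whole dialysis sessions;
- the 10–15 minute game sessions;
- rooms or seating within one dialysis period;
- measurement sessions;
- a partial split of the timetable.

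Only whole dialysis sessions holding one arm each lead to the full problem.

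**2. Could complete separation arise by chance?** With n patients per arm in 2k equal dialysis sessions, the chance that every session holds a single arm is C(2k, k) / C(2n, n).
- n = 10, k = 2: 6 / 184,756 = 3.2 × 10⁻⁵.
- n = 18, k = 3: 20 / C(36, 18) = 2.2 × 10⁻⁹.

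So chance is ruled out. But the sentence describes deliberate separation, so these figures do not help to decide which reading is right.

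**3. Error rate if each dialysis session held one arm.** The simulation used a normal post-treatment score, no treatment effect, a session effect with variance equal to the intraclass correlation (ICC), and a two-sided Mann–Whitney test at 0.05 (60,000 replicates).

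| Assumed layout | ICC 0 | 0.01 | 0.02 | 0.05 |
|---|---|---|---|---|
| 30 per arm, one session per arm | 4.9% | 7.9% | 11.3% | 20.7% |
| 30 per arm, three sessions per arm | 4.9% | 5.9% | 6.8% | 9.9% |
| 18 per arm, three sessions per arm | 4.7% | 5.3% | 5.8% | 7.4% |

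A hand check uses the variance ratio 1 + mρ/(1 − ρ), with m patients per session and ρ the ICC. For m = 30/3 = 10 and ρ = 0.05 this is 1 + 10 × 0.05/0.95 = 1.526, and the error rate is 2[1 − Φ(1.960/√1.526)] = 11.3%. That is somewhat above the simulated 9.9%, because the formula leaves the spread between sessions out of the test's own variance.

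**4. Dependence on what is tested.** The table assumes a raw post-treatment score. The SAP plans repeated measures within each group, and H3 concerns a decrease, but it does not say whether the Mann–Whitney test is applied to scores or to changes. Write a score as Y = μ + s + e, where s is the session effect and e the patient-level error. If s is the same at both times, the change is e(after) − e(before), and s drops out. For 30 per arm, three sessions per arm and ICC 0.05, the simulated rate on change scores was 4.7% instead of 9.9%. Staff and time of day could well be stable in this way.

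**5. Would another analysis do better?** At 30 per arm and a difference of 0.74 SD (both assumed), a t-test on session mean ranks has these powers:
- two sessions per arm: 36% at ICC 0, 26% at ICC 0.05;
- three sessions per arm: 57% at ICC 0, 44% at ICC 0.05.

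The Mann–Whitney test at ICC 0 has 78%. With one session per arm, session and arm coincide and no analysis can separate them.

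**6. The missing variable.** SAP section 5 names four instruments only. It omits treatment arm and every baseline characteristic. Yet SAP section 4 plans percentages and chi-square or Fisher tests for categorical data, although none of the four instruments is named as categorical. The list is therefore not exhaustive, and a session variable missing from it is weak evidence that session was not recorded.

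**The case for a change.** The strongest argument for acting is that the dialysis reading is a natural one. Controls receive standard care and no game sessions are described for them, so separating the two arms' sessions most readily suggests their dialysis sessions. If that is what happened, the attribution problem needs no simulation: the arms would differ in session conditions as well as in the game. Change scores would not protect against session effects that vary over time. The remedy would also be cheap, namely a few sentences and one table. The protocol sentence is in the past tense, so the investigators should already know the answer.

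Much of this stands. The sentence is ambiguous, the separation would not arise by chance, and the attribution problem would be real under that reading. But the argument stays conditional throughout. It needs *sessions* to mean dialysis sessions, each session to hold one arm, session conditions to affect questionnaire scores, and that effect to reach the quantity tested. The documents establish none of the four. Even if all held, the Mann–Whitney test would remain the main analysis, and the consequence would be a limitation stated in the report.

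**Conclusion.** The wording in Protocol section 5 is unclear, but no error is shown and no change to the plan follows. The investigators know what was separated and can say so when they report the trial. If whole dialysis sessions turn out to have held one arm each, the report would say how patients came to be in them, tabulate session by arm, and note that session conditions and the game cannot be fully told apart. The planned test would be the same.

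No error rate can be given for this trial. Under the assumed layouts the nominal 5% could stay where it is or rise to 9.9% with three sessions per arm, or to 20.7% with one, at ICC 0.05. Those figures apply only to single-arm dialysis sessions and a raw post-treatment score. If the arms shared dialysis sessions, or outcomes are not correlated within session, the concern does not arise.

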### 1. Overview

This Statistical Analysis Plan (SAP) outlines the methods and procedures for the analysis of data collected from a randomized controlled trial investigating the effects of a story-based digital game intervention on treatment adherence, dietary knowledge, and anxiety among hemodialysis patients.

### 2. Objectives and Hypotheses

Primary Objective:

- To evaluate whether a story-based digital game intervention improves treatment adherence, dietary knowledge, and reduces anxiety in patients undergoing hemodialysis.

Hypotheses:

- H1: Patients receiving the digital game intervention will show higher adherence scores.
- H2: Patients receiving the intervention will demonstrate improved dietary knowledge.
- H3: Anxiety levels will decrease more significantly in the intervention group than in the control group.

### 3. Study Design Summary

This study follows a single-center, single-blinded, randomized controlled design with two parallel arms: an intervention group and a control group. Patients were randomized (1:1) to either group.

### 4. Statistical Methods

The analysis will follow the intention-to-treat principle. Descriptive statistics will be calculated for all variables. Continuous variables will be presented as mean  $\pm$  standard deviation, and categorical variables as frequencies and percentages.

Between-group comparisons of continuous variables will use the Mann–Whitney U test. Repeated measures within each group will be analyzed using the Friedman test. Post hoc analyses will be conducted using the Wilcoxon signed-rank test with Bonferroni correction where applicable. Chi-square or Fisher's exact tests will be used for categorical data.

Statistical significance will be determined at a two-sided alpha level of 0.05.

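### SAP 4 names Mann–Whitney for between-arm comparisons but not the assessment, the quantity or the hypothesis it decides, and its only repeated-measures methods are within-arm

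*SAP*

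**What the plan says.** SAP 4 has one sentence on comparing the arms on continuous outcomes: "Between-group comparisons of continuous variables will use the Mann–Whitney U test". The next two deal with change over time. The first of them reads "Repeated measures within each group will be analyzed using the Friedman test". The second adds the pairwise follow-up: "Post hoc analyses will be conducted using the Wilcoxon signed-rank test with Bonferroni correction where applicable". Alpha is fixed by "Statistical significance will be determined at a two-sided alpha level of 0.05".

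SAP 2 states three hypotheses. For adherence it says "H1: Patients receiving the digital game intervention will show higher adherence scores", with no comparator named. For diet knowledge the wording is "H2: Patients receiving the intervention will demonstrate improved dietary knowledge", again without a comparator. Only the anxiety hypothesis refers to the other arm: "H3: Anxiety levels will decrease more significantly in the intervention group than in the control group".

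SAP 3 describes "two parallel arms: an intervention group and a control group". SAP 5 matches each construct to a scale and goes no further. Protocol 8 lists adherence, diet knowledge and state anxiety as three primary measures. Protocol 9 repeats the test names, attaches Bonferroni to the Wilcoxon tests and defers to the SAP. SAP 6 promises a Bonferroni adjustment in general terms, without naming the family of tests. It calls the sample small and the scales ordinal, and gives that as the reason for non-parametric tests.

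The available text of the two documents gives no assessment schedule, no analysed quantity for the Mann–Whitney test, and no link from a test to H1, H2 or H3.

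**The concern.** A two-arm trial is decided by a between-arm comparison, and here that comparison is named only by its test. Friedman followed by post hoc pairs suggests at least three occasions. Several Mann–Whitney results per primary scale would therefore fit the sentence, and none is designated as deciding.

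Two things are at stake. First, the significance verdict on a scale can depend on a choice that the plan leaves to the analyst. If that choice is made after the results are seen, the false-positive rate can rise. Second, the methods that do address change are within-arm. H3 needs a comparison of change between arms, and H2 speaks of improvement with no comparator. A significant Wilcoxon test in the game arm could then be reported as support for the intervention although it says nothing about the control arm. H1 reads most naturally as a between-arm comparison of scores, but its assessment is open too.

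**Working it through.** The plan contains no sample size, effect, SD or power figure, so there is nothing to reproduce. The check sets the text against each hypothesis and then sizes the gap under stated assumptions.

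**1. Text against hypotheses**

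| | Comparator stated | Quantity implied | Assessment stated | Test linked |
|---|---|---|---|---|
| H1 adherence | no (implied by the two-arm design) | score | no | no |
| H2 diet knowledge | no (implied by the two-arm design) | unclear | no | no |
| H3 anxiety | control arm | decrease | no | no |

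**2. What the choice of quantity does to precision.** With equal SDs and baseline–final correlation r, the variance of the between-arm contrast relative to final score is 1 for final score, 2(1−r) for change and 1−r² for a baseline-adjusted score. Change beats final score only if 2(1−r) < 1, that is r > 0.5. The adjusted variance is never larger than either, since 1−r² ≤ 1 and 1−r² = (1−r)(1+r) ≤ 2(1−r).

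Normal-approximation power, assuming 30 per arm, 0.5 SD and two-sided alpha 0.05, is Φ(0.5·√(30/2)/√v − 1.96) = Φ(1.936/√v − 1.96):

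- Final score, v = 1: Φ(−0.02) = 49%.
- r = 0.3: change, v = 1.4, 37%; adjusted, v = 0.91, 53%.
- r = 0.7: change, v = 0.6, 70%; adjusted, v = 0.51, 77%.

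**3. The same by simulation with rank tests** (20,000 trials per setting, trivariate normal, 30 per arm, 0.5 SD, alpha 0.05). The adjusted test ranks both scores, regresses final ranks on baseline ranks, and compares residuals between arms.

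| Correlation | 0.2 | 0.4 | 0.6 | 0.8 |
|---|---|---|---|---|
| Final score | 46% | 46% | 46% | 46% |
| Change | 32% | 40% | 54% | 84% |
| Rank-based adjusted | 47% | 52% | 62% | 84% |

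With 7-level ordinal scores at correlation 0.4/0.6/0.8: final 44%/45%/44%, change 36%/49%/73%, adjusted 49%/58%/77%. The adjusted test kept its size with no effect (about 5%).

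**4. How often final-score and change tests give different verdicts** (30 per arm, correlation 0.6, continuous, alpha 0.05)

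| True effect | 0 | 0.25 SD | 0.5 SD | 0.8 SD | 1.0 SD |
|---|---|---|---|---|---|
| Different verdicts | 8% | 21% | 36% | 17% | 5% |

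**5. False positives from picking the best of four tests per scale** (score or change, at either of two post-baseline occasions; no treatment effect; 20–40 per arm, correlation 0.4–0.8, continuous and ordinal). A single fixed test rejects in 4.5%–5.2%.

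| Bonferroni covers | Alpha per test | Rejects per scale | Benchmark per scale |
|---|---|---|---|
| no between-arm test | 0.05 | about 16% | 5% |
| the three scales only | 0.05/3 = 0.0167 | 5.4%–5.8% | 1.67% |
| all four tests on a scale | 0.05/4 = 0.0125 | 4.0%–4.4% | 5% |
| all twelve tests | 0.05/12 = 0.0042 | 1.2%–1.5% | 1.67% |

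**6. Reading within-arm tests as efficacy.** Assume the same true change in both arms (0.3–0.5 SD, correlation 0.5, 20–40 per arm; 4,000 trials per setting). The Wilcoxon test at 0.05 is significant in exactly one arm in 25%–50% of trials, and in the game arm alone in 13%–25%. Mann–Whitney on change rejects in about 4%–5%.

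**The case against.** Mann–Whitney is the only between-arm test named for continuous variables, so it must serve any between-arm reading of H1–H3. A reader might infer that the SAP has no test for H3. It does not support that: nothing prevents applying Mann–Whitney to change. The fault is under-specification.

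The wording of the hypotheses also narrows the choice: H1 points to scores and H3 to change. This stands, and it means that the quantity is not equally open on all three scales. It leaves the assessment open on all three and the quantity unclear for H2.

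A reader might infer that two analysts could reach opposite conclusions. They would not. At 0.5 SD and 30 per arm, the two tests were significant in opposite directions in at most 0.01% of simulated trials. Where their verdicts differed, the estimated direction agreed in 96%–98%. Nor is frequent disagreement a general fact. It peaks near 0.5 SD in the settings tried, and the documents give no effect size.

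A reader might also take 16% as the trial's error rate. SAP 6, read plainly, promises Bonferroni for multiple testing without limit, and full coverage removes the inflation. The 16% needs the narrower reading suggested by SAP 4 and Protocol 9. Even full coverage, however, would not say which result decides each hypothesis.

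Finally, naming any one quantity and assessment in advance would close the specification gap. Baseline adjustment is a better choice of method, not the correction of an error.

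**Conclusion.** The concern holds as an under-specified confirmatory comparison that should be fixed. It is clearest for H3, for H2 and for the unnamed deciding assessment. That part rests on the text alone.

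Its size rests on assumed sample size, effect, correlation and number of occasions. The significance verdict may turn on the unstated quantity in about 5% to 36% of trials, depending on the true effect. Choosing among tests causes no inflation if Bonferroni covers every between-arm test run. It roughly triples the per-scale error if Bonferroni covers none of them (16% against 5%) or only the three scales (about 5.5% against 1.67%). The documents do not settle which applies. The separate risk of citing a within-arm result as efficacy remains until the plan excludes it.

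**What to change.** - Word H1–H3 as game versus control. For H3, for example: the decrease in State Anxiety from baseline to [one stated assessment] is larger in the game arm than in the control arm.
- For each primary scale, name one between-arm confirmatory test at one stated post-baseline assessment: the rank-based baseline-adjusted comparison in step 3 of the working. It keeps the non-parametric rationale of SAP 6 and uses the baseline that H3 and the repeated measures imply. In the settings tried, its power matched or exceeded that of both alternatives.
- Mann–Whitney on change is a weaker fallback, because it has less power than final score when the correlation is below about 0.5.
- State which tests the Bonferroni correction covers.
- State that the within-arm Friedman and Wilcoxon results, and other time points, are descriptive and do not support H1–H3.
- If outcome data have already been seen, date and disclose the change.

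This is a cheap improvement: SAP wording and a little more analysis work for the adjusted rank test, with no new patients, visits or procedures. The downside is that favourable within-arm or other-visit results can no longer be cited as evidence of efficacy.

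### The only between-arm test of the three primary scales cannot use the pre-intervention score; a rank analysis of covariance would gain precision at almost no cost

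*SAP*

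**What the plan says.** SAP section 4 gives one between-arm method for the scales: "Between-group comparisons of continuous variables will use the Mann–Whitney U test". The repeated scores are used only inside each arm: "Repeated measures within each group will be analyzed using the Friedman test", followed by Wilcoxon signed-rank tests as post hoc comparisons. Protocol section 9 lists the same set: "Non-parametric methods (Mann-Whitney U, Friedman test) and Bonferroni-corrected Wilcoxon tests will be used". Neither document names a baseline covariate, an analysis of covariance (parametric or rank-based) or a mixed model. Neither says whether the Mann-Whitney is applied to final scores or to changes.

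SAP section 6 gives the reason for the choice: "Given the small sample size and the ordinal nature of the scales used, non-parametric tests were selected". It adds that "Multiple testing adjustments will be made using Bonferroni correction", without defining the family of tests. Protocol section 8 lists three primary scales (adherence, diet knowledge, state anxiety).

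No assessment schedule is given. That a pre-intervention score exists is an inference from two places: the Friedman test needs repeated scores, and SAP section 2 states "H3: Anxiety levels will decrease more significantly in the intervention group than in the control group", which needs a starting value.

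**The concern.** In a randomized trial with a pre-intervention score on the same scale, that score is usually the best available predictor of the final score. A plain two-sample rank test either ignores it (final scores) or fixes its coefficient at 1 (change scores). Neither is generally the most precise use of it.

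Precision is scarce here. The SAP itself calls the sample small, there are three primary scales, and a Bonferroni correction may lower the threshold for each. If the baseline score is collected and left out of the between-arm test, H1, H2 and H3 are each tested with less power than the same patients could provide.

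**Working it through.** **Inputs from the documents.** Two-sided alpha 0.05 (SAP section 4); 1:1 allocation (SAP section 3); Bonferroni with no stated family (SAP section 6). If the family is the three primary scales, the per-scale alpha is 0.05/3 = 0.0167. There is no planned power or sample size to reproduce.

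**Assumptions.** Pre/post correlation r from 0.3 to 0.8; unadjusted power P from 50% to 90%; equal variance before and after.

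**Formula.** Relative to the final-score variance, the variance v is 1 for final scores, 2(1 − r) for change scores and 1 − r² with baseline as covariate. If the final-score test has power P, a test with relative variance v has power Φ((z_α + z_P)/√v − z_α).

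**Example.** r = 0.5, P = 80%, alpha 0.05: v = 1 − 0.25 = 0.75, so the variance falls by 25%. Power is Φ((1.960 + 0.842)/0.866 − 1.960) = Φ(1.275) = 89.9%, a gain of 9.9 points. For change scores v = 2(1 − 0.5) = 1, so power stays at 80% and the gain over change is also 9.9.

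**By unadjusted power, r = 0.5** (gain in points, the same over final and change scores at this correlation):

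| Unadjusted power | Alpha 0.05 | Alpha 0.0167 |
|---|---|---|
| 50% | 11.9 | 14.4 |
| 60% | 12.4 | 14.6 |
| 70% | 11.8 | 13.5 |
| 80% | 9.9 | 11.0 |
| 90% | 6.3 | 6.8 |

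**By correlation, final-score power 80%, alpha 0.05** (gains taken before rounding the powers):

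| r | Change | Adjusted | Gain over final | Gain over change |
|---|---|---|---|---|
| 0.3 | 65.8% | 83.6% | 3.6 | 17.7 |
| 0.5 | 80.0% | 89.9% | 9.9 | 9.9 |
| 0.7 | 95.1% | 97.5% | 17.5 | 2.4 |
| 0.8 | 99.3% | 99.7% | 19.7 | 0.3 |

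**Simulation of the rank tests.** The formula describes covariate adjustment in general, so the rank tests themselves were simulated (bivariate normal scores, 10,000 runs per scenario, alpha 0.05, 30 per arm, standardized difference 0.75):

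| r | Mann-Whitney, final | Mann-Whitney, change | Quade |
|---|---|---|---|
| 0.3 | 80.0% | 65.8% | 82.7% |
| 0.5 | 79.7% | 79.7% | 88.4% |
| 0.7 | 79.6% | 94.8% | 96.1% |
| 0.8 | 79.3% | 99.3% | 99.2% |

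At r = 0.5 the gain is 88.4 − 79.7 = 8.7 points, slightly below the formula's 9.9. With 20 per arm and a difference of 0.8 at r = 0.5, the powers are 65.5%, 65.6% and 75.9%. At alpha 0.0167, with 30 per arm, a difference of 0.75 and r = 0.5, they are 63.8%, 64.4% and 76.9%. A separate simulation with scores rounded to whole numbers (4,000 runs per cell; 20, 30 or 40 per arm) gave null rejection of 4.6% to 5.6% for Quade's test, so no inflation of note was seen.

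**The case against.** The strongest reply is that the plan contains no mistake here. The Mann-Whitney is simple, keeps its type I error under randomization, and is justified in SAP section 6. That stands, and it limits the point to efficiency. It does not justify leaving out the baseline: small samples and ordinal scales argue against normal-theory models, and a rank-based adjusted test meets the same reason. Change scores sit less easily with it, because they subtract ordinal values.

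A second reply is that the size is unknown. That also stands. A reader might infer that the trial loses about 9 points of power on each scale, whichever quantity is tested. The documents do not support that. The figure needs correlation 0.5, about 80% unadjusted power and alpha 0.05; only the alpha is stated, and Bonferroni may lower it. The equality of the two losses is particular to r = 0.5, where 2(1 − r) = 1. If the Mann-Whitney is applied to changes, as H3 suggests for anxiety, the loss could be large (r = 0.3) or negligible (r = 0.8). In very small arms Quade can even fall slightly behind change scores: with 15 per arm, a difference of 0.8 and r = 0.8, 89.2% against 90.7%. The equality also depends on score shape. With a ceiling at +0.5 SD (r = 0.5, 30 per arm), final scores gave 71%, change scores 52% and Quade 80%.

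A third reply is that Quade's test needs one baseline and one outcome, while a Friedman test with post hoc pairs implies three or more occasions. This is correct, so the fix must name the time points.

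Finally, a reader might infer that chance baseline imbalance biases the planned comparison. It does not: over repeated randomization the imbalance adds noise, which the unadjusted test already allows for.

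**Conclusion.** The point holds as a matter of precision. The planned between-arm test leaves out a baseline score that the plan very probably collects, and a rank-based alternative within the plan's own rationale would use it.

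At correlation 0.5, adjustment is worth a 25% cut in variance, or about a quarter fewer patients for the same power. By formula that is about 6 to 12 points of power at alpha 0.05 and about 7 to 15 at 0.0167. At 80% unadjusted power and alpha 0.05 it is about 10 points by formula and about 9 for Quade in simulation. Away from correlation 0.5 the gain depends strongly on whether final or change scores would otherwise be tested.

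All of these sizes rest on assumed correlations and power and on near-normal scores, and the baseline assessment is itself inferred. The planned test is not invalid, so this is a free or cheap improvement rather than a correction.

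**What to change.** In SAP section 4, with a matching line in Protocol section 9:

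1. For each of the three primary scales, state the baseline assessment and one primary post-intervention assessment.
2. Make Quade's rank analysis of covariance the between-arm test. Rank the post-intervention scores over both arms together, do the same for the pre-intervention scores, regress the first ranks on the second, and compare the residuals between arms.
3. Keep the unadjusted Mann-Whitney as a sensitivity analysis, and say whether it uses final or change scores.
4. State a rule for patients without a baseline score, for example the overall median baseline rank.
5. Date the change before any unblinded analysis. Protocol section 1 places the study in March and April 2025, and SAP section 3 reports randomization in the past tense ("Patients were randomized (1:1) to either group"), so data may already be in hand. Protocol section 5 has the statistician blinded, which leaves room for a dated change if no comparison by arm has yet been made.

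GAMEX is unaffected, since it is measured only in the game arm.

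The cost is a short addition to the SAP, one protocol line and a few extra SPSS v26 steps (rank, regression, one-way ANOVA). If the inferred baseline is collected, no new patients, visits or data are needed.
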